**8.1.3. Solicited adverse events**

The term “reactogenicity” refers to solicited signs and symptoms (“solicited AEs”) occurring in the hours and days following a vaccination, to be collected by the subjects/parent(s)/LAR(s) for 7 consecutive days, using a pre-defined Subject Diary.

The following solicited AEs are included in the Subject Diary.

**8.1.3.1.     Solicited local adverse events**

Solicited local (injection site) AEs for this study are pain, erythema, swelling, and induration. The preferred location for measuring temperature in this study is the axilla. Solicited local AEs will be recorded and collected according to which vaccine was administered and the site of administration (e.g. upper or lower deltoid and the arm used for administration).

**8.1.3.2.    Solicited systemic adverse events**

Solicited systemic AEs for this study are fever (body temperature  $\geq 38.0^{\circ}\text{C}$ ), nausea, myalgia, arthralgia, headache, and fatigue.

**8.1.3.3.    Other solicited adverse events**

The use of analgesics/antipyretics (preferably paracetamol) for either prophylactic or treatment purposes will also be recorded as other solicited events in the Subject Diary and verified onto specific eCRFs and subject medical records.

The study staff must review the data entered into the Subject Diary as described in Section [11.2](#).

Note: Any solicited AE that meets any of the following criteria must be entered into subjects' source document (see Section [11.2](#)) and also as an AE event on the Adverse Event eCRF:

- Solicited local or systemic AE that continues beyond day 7 after vaccination.
- Solicited local or systemic AE that leads to a visit to a healthcare provider (medically attended AE, see Section [8.3.3.4](#)).
- Solicited local or systemic AE leading to the subject withdrawing from the study or the subject being withdrawn from the study by the investigator (AE leading to withdrawal).
- Solicited local or systemic AE that otherwise meets the definition of an SAE (see Section [8.1.2](#)).

**8.1.4.     Unsolicited adverse events**

An unsolicited AE is an AE that was not solicited using a Subject Diary and that was spontaneously communicated by a subjects/parent(s)/LAR(s) who has signed the informed consent or a solicited local or systemic AE that continues beyond the solicited period at day 7 after vaccination.

Unsolicited AEs will be collected during interview with the subjects/parent(s)/LAR(s) and by review of available medical records at the next visit. Unsolicited AEs will be reviewed at the safety follow-up calls as well.

Subjects/parent(s)/LAR(s) will be instructed to contact the site as soon as possible to report potential unsolicited AEs that required hospitalization, emergency room visit, or

visit to/by a health care provider that were of concern to the subjects/parent(s)/LAR(s). The detailed information about the reported unsolicited AEs will be collected by qualified site personnel during the interview and will be documented in the subject's records. Unsolicited AEs (including those of concern to subjects/parent(s)/LAR(s) and those which led to a medical visit but were not of concern) will be collected during the visit interview.

Unsolicited AEs that are not medically attended nor perceived as a concern by subjects/parent(s)/LAR(s) will be collected during interview with the subjects/parent(s)/LAR(s) and by review of available medical records at the next visit.

#### **8.1.5. Clinical laboratory parameters and other abnormal assessments qualifying as adverse events or serious adverse events**

Only immunogenicity blood samples will be collected in this study (i.e. no routine clinical laboratory assessments will be performed per protocol). Should any local laboratory tests be performed during the study for a subject, AEs will be recorded as follows.

In absence of diagnosis, abnormal laboratory findings (e.g. clinical chemistry, hematology, urinalysis) or other abnormal assessments that are judged by the investigator to be clinically significant will be recorded as an AE or SAE if they meet the definition of an AE or SAE (refer to Sections 8.1.1 and 8.1.2). Clinically significant abnormal laboratory findings or other abnormal assessments that are present at baseline and significantly worsen following the start of the study will also be reported as AEs or SAEs. However, clinically significant abnormal laboratory findings or other abnormal assessments that are associated with the disease being studied, unless judged by the investigator as more severe than expected for the subject's condition, or that are present or detected at the start of the study and do not worsen, will not be reported as AEs or SAEs.

The investigator will exercise his or her medical and scientific judgement in deciding whether an abnormal laboratory finding or other abnormal assessment is clinically significant.

#### **8.1.6. Adverse events of special interest**

Adverse events of special interest are predefined (serious or non-serious) AEs of scientific and medical concern specific to the product or program, for which ongoing monitoring and rapid communication by the investigator to the sponsor can be appropriate, because such an event might warrant further investigation in order to characterize and understand it.

Arthritis is the only AESI in this study as described in Section 1.3.1 and Section 8.1.6.1.

##### **8.1.6.1. Arthritis**

Cases of arthritis are defined according to the following ad-hoc definition:

- Presence of physical examination findings of swelling, redness, heat, or limitation in range of motion  
and/or
- Presence of diagnostic imaging studies interpreted by a health care provider as demonstrating evidence of joint inflammation and/or arthrocentesis results evidencing inflammation

Due to the heterogeneity of the presentation of arthritis, which can be either acute or chronic, the threshold of duration of 6 weeks is to be considered.

The list of preferred terms corresponding to the diagnosis of arthritis are those included in the Medical Dictionary for Regulatory Activities (MedDRA) Standardized MedDRA Queries Narrow “Arthritis.” For any new diagnosis of arthritis (serious or non-serious) in a study subject, the investigator (or designate) must complete an electronic Expedited Adverse Events Report and an ad-hoc eCRF page on arthritis to further characterize this AESI.

## **8.2. Events or outcomes not qualifying as adverse events or serious adverse events**

### **8.2.1. Pregnancy**

Female subjects who are pregnant or lactating at the time of vaccination must not receive additional doses of study vaccine(s) but may continue other study procedures at the discretion of the investigator.

While pregnancy itself is not considered an AE or SAE, any adverse pregnancy outcome or complication or elective termination of a pregnancy for medical reasons will be recorded and reported as an AE or an SAE.

Note: The pregnancy itself should always be recorded on a paper pregnancy report.

The following should always be considered as SAEs and will be reported as described in Sections 8.4.1 and 8.4.3:

- Spontaneous pregnancy loss, including:
  - spontaneous abortion, (spontaneous pregnancy loss before/at 22 weeks of gestation)
  - ectopic and molar pregnancy
  - stillbirth (intrauterine death of fetus after 22 weeks of gestation).

Note: the 22 weeks cut-off in gestational age is based on the World Health Organization-International Classification of Diseases 10 noted in the European Medicines Agency guideline on pregnancy exposure [EMA, 2006]. It is recognized that national regulations might be different.

- Any early neonatal death (i.e. death of a live born infant occurring within the first 7 days of life).
- Any congenital anomaly or birth defect (as per [CDC MACDP](#) guidelines) identified in the offspring of a study subject (either during pregnancy, at birth or later) regardless of whether the fetus is delivered dead or alive. This includes anomalies identified by prenatal ultrasound, amniocentesis or examination of the products of conception after elective or spontaneous abortion.

Furthermore, any SAE occurring as a result of a post-study pregnancy AND considered by the investigator to be reasonably related to the study vaccine(s) will be reported to PPD as described in Section [8.4.3](#). While the investigator is not obligated to actively seek this information from former study participants, he/she may learn of a pregnancy through spontaneous reporting.

### **8.3. Detecting and recording adverse events, serious adverse events, and pregnancies**

#### **8.3.1. Time period for detecting and recording adverse events, serious adverse events, and pregnancies**

The time period for collecting and recording AEs will begin at the time of informed consent signature and through study discharge.

All AEs starting within 30 days following administration of each dose of study vaccine(s) must be recorded into the subject records and the appropriate section of the eCRF, irrespective of intensity or whether or not they are considered vaccination-related.

The time period for collecting and recording SAEs will begin at the time of informed consent signature and will end 30 days following administration of the last dose of study vaccine(s) for each subject. See Section [8.4](#) for instructions on reporting of SAEs.

All medically attended AEs will be collected and recorded from the time of informed consent signature.

All AEs/SAEs leading to withdrawal from the study will be collected and recorded from the time of informed consent signature.

In addition to the above-mentioned reporting requirements and in order to fulfil international reporting obligations, SAEs that are related to study participation (i.e. protocol-mandated procedures, invasive tests, a change from existing therapy) or are related to a concurrent GSK medication/vaccine will be collected and recorded from the time the subject consents to participate in the study until she/he is discharged from the study.

The time period for collecting and recording pregnancies will begin at the time of informed consent signature and will end 30 days following administration of the last dose of study vaccine(s). See Section [8.4](#) for instructions on reporting of pregnancies.

The time period for collecting and recording of AESIs will begin at the time of informed consent signature and will end 30 days following administration of the last dose of study vaccine(s). See Section [8.4](#) for instructions on reporting of AESIs.

An overview of the protocol-required reporting periods for AEs, SAEs, and pregnancies is given in [Table 11](#).

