### 4.2. Inclusion criteria for enrollment

Deviations from inclusion criteria are not allowed because they can potentially jeopardize the scientific integrity, regulatory acceptability of the study, or subject safety. Therefore, adherence to the criteria as specified in the protocol is essential.

All subjects must satisfy ALL the following criteria at study entry:

1. Subjects and/or subjects' parent(s)/Legally Acceptable Representative(s) (LARs) who, in the opinion of the investigator, can and will comply, with the requirements of the protocol (e.g. completion of the pDiary, return for follow-up visits, availability for all visits scheduled in the study).
2. Written informed consent obtained from the subject and/or from the parent(s)/LAR(s) of the subject prior to performing any study specific procedure.
3. Written informed assent obtained from subjects below the legal age of consent prior to performing any study specific procedure.
4. A male or female between, and including, 10 to 25 years of age at the time of the first vaccination.
5. Healthy subjects as established by medical history and clinical examination before entering into the study.
6. Female subjects of non-childbearing potential may be enrolled in the study.
  - Non-childbearing potential is defined as pre-menarche, current bilateral tubal ligation or occlusion, hysterectomy, or bilateral ovariectomy.

Please refer to the [glossary of terms](#) for the definition of menarche.

7. Female subjects of childbearing potential may be enrolled in the study, if the subject:
  - has practiced highly effective for 30 days prior to vaccination, and
  - has a negative pregnancy test on the day of vaccination, and
  - has agreed to continue highly effective contraception during the entire treatment period and for 2 months after completion of the vaccination series.

Please refer to the [glossary of terms](#) for the definition of highly effective contraception.

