## 6.5. Contraindications to subsequent vaccination

The following events constitute absolute contraindications to further administration of MenABCWY, rMenB+OMV NZ, or MenACWY. If any of these events occur during the study, the subject must not receive additional doses of vaccine(s) but may continue other study procedures at the discretion of the investigator (see Section 8.5).

- Anaphylaxis following the administration of vaccine(s).
- Pregnancy (see Section 8.2.1).
- Any occurrence of an event listed in the exclusion criteria, which must always be re-assessed by the investigator before administration of the second dose of study vaccine(s). Refer to Section 4.3.
- Subjects who experience any SAE judged to be possibly or probably related to study vaccine(s), including hypersensitivity reactions.
- Subjects who develop any new condition which, in the opinion of the investigator, may pose additional risk to the subject if he/she continues to participate in the study.
- Any condition that in the judgment of the investigator would make IM injection unsafe.

The following events constitute contraindications to administration of MenABCWY, rMenB+OMV NZ, or MenACWY at that point in time; if any of these events occur at the time scheduled for vaccination, the subject may be vaccinated at a later date, within the time window specified in the protocol (see Section 5.5).

- Body temperature elevation (i.e. fever) within 3 days prior to intended study vaccination. Fever is defined as temperature  $\geq 38.0^{\circ}\text{C}$ .
- Significant acute illness (e.g. acute severe febrile illness) within 7 days prior to vaccination.
- Administration of any other vaccine 14 days (for inactivated vaccines), 28 days (for live vaccines), or 7 days (for influenza vaccines) prior to vaccination.

Additionally, the following event warrants the delay of blood sample collection for immunogenicity assessments in this study.

- Receipt of systemic antibiotics with the previous 3 days before blood sample collection.

In the event that a subject meets the criterion for delay of blood sample collection, blood sample collection may proceed once the appropriate window for delay has passed.

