### **8.4. Reporting of serious adverse events, pregnancies, and other events**

#### **8.4.1. Prompt reporting of serious adverse events, pregnancies, and other events**

Serious AEs that occur in the time period defined in Section 8.3 will be reported promptly to PPD within the timeframes described in [Table 13](#), once the investigator determines that the event meets the protocol definition of a SAE.

Pregnancies that occur in the time period defined in Section 8.3 will be reported promptly to PPD within the timeframes described in [Table 13](#), once the investigator becomes aware of the pregnancy.

Adverse events of special interest that occur in the time period defined in Section 8.3 will be reported promptly to PPD within the timeframes described in Table 13, once the investigator determines that the event meets the protocol definition of an AESI.

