## Safety Endpoints

- Solicited local and systemic AEs in all study groups
  - Occurrence of solicited local and systemic AEs during the 7 days (including the day of vaccination) after each vaccination (Day 1 to Day 7 and Day 61 to Day 67 [Day 1 to Day 7 only for subjects in the MenACWY group])
- Unsolicited AEs in all study groups
  - Occurrence of unsolicited AEs during the 30 days (including the day of vaccination) after each vaccination (Day 1 to Day 31 and Day 61 to Day 91 [Day 1 to Day 31 only for subjects in the MenACWY group])
- SAEs, medically attended AEs, AEs leading to withdrawal, and AESIs, in all study groups from informed consent signature to Visit 4 (Day 91)

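### Protocol 8.3.1 ends SAE and AESI collection 30 days after the last dose, which contradicts the Day 91 endpoint, most clearly for subjects who stop after dose 1

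*Protocol*

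**What the plan says.** Protocol 8.3.1 gives different ends for different event types:

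- **SAEs:** collection "will end 30 days following administration of the last dose of study vaccine(s) for each subject".
- **AESIs:** counted from the last dose, "The time period for collecting and recording of AESIs will begin at the time of informed consent signature and will end 30 days following administration". The words on each subject are absent here.
- **Pregnancies:** the same 30-day end, counted from the last dose and again without those words: "The time period for collecting and recording pregnancies will begin at the time of informed consent signature and will end 30 days following administration".
- **AEs in general:** "The time period for collecting and recording AEs will begin at the time of informed consent signature and through study discharge".
- **SAEs linked to study participation or to a concurrent product of the sponsor:** until discharge.

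Protocol 8.4.1 then makes the 8.3 period the condition for prompt reporting. For pregnancies it reads "Pregnancies that occur in the time period defined in Section 8.3 will be reported promptly", and SAEs and AESIs have parallel sentences.

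The secondary safety endpoint in Protocol 10.2 covers "SAEs, medically attended AEs, AEs leading to withdrawal, and AESIs, in all study groups from informed consent signature to Visit 4 (Day 91"). SAP 3.2.2 repeats it. Protocol Table 4 marks SAE and AESI recording at Visit 3, Safety Call 2 and Visit 4. SAP 3.1 records these events through Visit 4, but through Visit 2 in the MenACWY group.

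The protocol expects some subjects to miss dose 2 and remain in the study. Under 6.5, after a listed event, "the subject must not receive additional doses of vaccine(s) but may continue other study procedures at the discretion of the investigator". Section 9.2.2 says the same of withdrawal from vaccine in general.

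**The concern.** The end of the SAE period moves with the subject's last dose, while the endpoint ends at a fixed visit. The two separate when a subject in a two-dose group does not get dose 2. Among the reasons in 6.5 for withholding it are anaphylaxis and a related SAE, so subjects stopped for safety would have the shortest stated period for new SAEs and AESIs.

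A site that follows the 30-day sentences could leave out, or not expedite, an event that belongs to the endpoint. The analysis would not show the omission. SAP Section 4 bases percentages on all subjects in the group within the analysis set. SAP 4.3 reduces the denominator only when at least 20% of subjects lack the data and the groups differ by Fisher's exact test. An unrecorded SAE in one stopped subject would normally appear as no event.

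**Working it through.** **Inputs.** Doses on Day 1 and Day 61 (Protocol Section 3). Collection ends at last dose + 30 days (8.3.1). Visit 3 is allowed on Days 54 to 71, and Visit 4 is allowed 23 to 40 days after Visit 3 (Table 5). The endpoint ends at Day 91 (10.2).

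**1. The plan's own day count.** For unsolicited AEs, 10.2 maps the 30 days after each dose to Days 1–31 and Days 61–91. Dose day + 30 gives 1 + 30 = 31 and 61 + 30 = 91, so the mapping is reproduced. For a subject exactly on schedule with both doses, 8.3.1 and the endpoint agree at Day 91.

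**2. Subject who stops after dose 1 and stays in follow-up.**
- End of the literal period: 1 + 30 = Day 31.
- Distance to the endpoint's end: 91 − 31 = 60 days.
- Distance to Visit 3: 61 − 31 = 30 days nominally; 54 − 31 = 23 to 71 − 31 = 40 days over the window.
- If both visit windows are used in full, Visit 4 falls between Day 54 + 23 = 77 and Day 71 + 40 = 111, which is 46 to 80 days after Day 31.

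**3. Subject who receives both doses.** The period ends 30 days after dose 2 and Visit 4 falls 23 to 40 days after it. At the late end the period closes 40 − 30 = 10 days before Visit 4. At the early end Visit 4 comes 30 − 23 = 7 days before the period closes. Neither end date alone covers both cases; the later of the two does.

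**4. MenACWY group (about 100 subjects, one dose).** 8.3.1 gives 1 + 30 = Day 31, and SAP 3.1 stops at Visit 2. The endpoint nevertheless names all study groups and Day 91, as does SAP 9.1.3 for AESIs in each study group. The difference is again 60 days, here by design and not through early stopping.

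**5. One event under each rule.** Take a new vaccine-related SAE on Day 45 in a subject who stopped after dose 1 and still attends:

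| Rule | Day 45 SAE |
|---|---|
| 8.3.1, SAE sentence | outside (45 > 31) |
| 8.3.1, general AE sentence | inside, to discharge |
| Table 4 | recorded at the next contact, Visit 3 |
| 10.2 and SAP 3.1 | inside, to Visit 4 |
| 8.4.1 | prompt report not required, because outside the 8.3 period |
| 8.4.3 | report within 24 hours of awareness, no period named |

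Had the same SAE been caused by the blood draw, 8.3.1 itself would collect it until discharge. The rules do not give one answer.

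**The case against.** The strongest reply is that collection does not in fact stop at Day 31. An SAE is an AE, and 8.3.1 collects AEs to discharge. It also collects medically attended AEs with no stated end, which would catch any hospitalization. Table 4 marks SAE and AESI recording, and vaccine-related SAEs separately, at every later contact. The safety calls cover SAEs and AESIs (5.6.13.3). Sections 8.4.3 and 8.4.5 set a 24-hour deadline from awareness without naming a period, and events already recorded are followed up (8.5.1). Much of this stands. It makes loss of data less likely, but it does not remove the two 30-day sentences or the condition in 8.4.1.

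Four stronger readings are tempting and are not supported:

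- **That 60 of 91 endpoint days (66%) lie outside mandatory collection.** This treats one sentence as controlling and ignores Table 4, the general AE sentence and SAP 3.1. The 60 days measure a contradiction, not a proven gap in data.
- **That a pregnancy found by the Visit 3 test goes unreported.** 8.2.1 has every pregnancy recorded on a paper report, 8.4.4 requires the report within 2 weeks of awareness, and 8.5.2 follows it to outcome. 8.4.1 also turns on when a pregnancy occurs, not when it is found, so one that began by Day 31 is inside the period. Pregnancy is not part of the Day 91 endpoint.
- **That 8.3.2 excuses sites from looking for these events.** It speaks of former participants and of events learned of after discharge; the subjects at issue are still in the study.
- **That the affected number can be stated.** An assumed 3% to 8% stopping after dose 1 would give 12 to 32 of 400 two-dose subjects, but the documents give no such rate, and the count would include subjects who leave the study altogether, for whom 8.3.1 changes nothing.

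**Conclusion.** The concern holds as an internal contradiction. The SAE and AESI sentences of 8.3.1, with 8.4.1 behind them, disagree with the endpoint in 10.2, with Table 4, with SAP 3.1 and with the general AE sentence of 8.3.1. The difference is 60 days for a subject who stops after dose 1 and stays in follow-up, and up to 10 days for a subject who receives both doses. The MenACWY group has a separate mismatch between the endpoint's Day 91 and the SAP's Visit 2. Endpoint events or prompt reports may be lost; the documents do not establish that they would be.

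Two conditions apply. Last dose is read as the last dose that the subject actually received, which the SAE sentence supports by referring to each subject and which is an inference for AESIs. The row marks of Table 11, by which 8.3.2 defines the reporting period, are not readable in the text available, so Table 11 is not used as evidence for either side.

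For pregnancy the finding is only that the 30-day period in 8.3.1 and 8.4.1 does not fit 8.2.1 and 8.4.4.

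**What to change.** - **Two-dose groups.** In 8.3.1, state that SAE and AESI collection runs to study conclusion (Visit 4) or to 30 days after the last dose, whichever is later, and that this includes subjects who stop vaccination but stay in the study. Change Table 11 as well if it follows 8.3.1. Section 8.4.1 then needs no separate change for SAEs and AESIs, because it refers to 8.3.
- **MenACWY group.** State one end of SAE and AESI collection for this group, and use it in Protocol 10.2, Table 4, and SAP 3.1, 3.2.2 and 9.1.3.
- **Pregnancy.** Reconcile the 30-day period in 8.3.1 and 8.4.1 with 8.2.1 and 8.4.4, so that a pregnancy found at the Visit 3 test is clearly reportable.

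For the two-dose groups the cost is wording, since the visits, calls and forms are already in Table 4. The downside is a few more expedited reports. If Day 91 were kept for the MenACWY group, the SAP's Visit 2 end would have to be extended; otherwise only the endpoint wording changes.
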